MRC START in [host trial name]: What are the effects of a re-written and re-designed Participant Information Sheet? A randomised controlled trial

[Protocol Version x.x] [DATE]

1. Background

In the UK, the NIHR vision sees 'more patients and health professionals participating in health research'[1]. Fundamental to health research is the testing of interventions through RCTs. Achieving high participation in RCTs has traditionally been difficult. Published data show that a minority of RCTs recruit successfully [2,3]. Recruitment problems reduce the total recruited sample (limiting internal validity), and the proportion of eligible participants who are recruited (limiting external validity).

Clearly, there is a need to develop and test interventions to improve recruitment, and one method is to 'nest' trials of recruitment interventions in ongoing randomised trials. Given the consensus among the research community concerning the challenge of recruitment, it is surprising that nested trials of recruitment interventions are so rare. Two recent reviews identified only 14 nested studies in real trials[4] and 27 overall [5]. Recruitment for science is not underpinned by a science of recruitment.

The MRC START study is designed to develop the conceptual, methodological and logistical framework for nested studies, and to assess their feasibility. At the completion of MRC START, we will have rigorously tested two potential interventions for adoption in to routine practice (improved PIS, and a multimedia decision aid), and provided the framework to make delivery of nested recruitment RCTs a routine activity. This will assist the rapid development of recruitment to meet policy goals [12]. [Host trial] is acting as a host trial to test an MRC START recruitment intervention. This protocol details the work that will be undertaken for MRC START in [Host trial].

2. The intervention – Participant information sheets

Research has reported patients' rather patchy understanding at the end of a trial, such as one in five participants not knowing the name of the medicine being tested [6] and similar proportions not knowing that they could withdraw at any time [7]. These findings are confirmed by a systematic review of consent in cancer trials [8] in which aspects such as treatment risks and benefits and the right to withdraw consent, were found to be not well understood. The review concluded that "patients do not appear to be adequately informed" (p.304). A lack of participant knowledge might result from the difficulty in understanding complex information, such as randomisation [9], or because of the way the Participant Information Sheet (PIS) is written. The level of literacy required to understand a study PIS is often higher than that found within the general population [10], and poor information provision may particularly affect older or less educated patients [11].

One promising approach to improving the quality of the written information provided is to develop the PIS through User Testing. In this process people in the target group for the trial read the PIS and are then asked to find and show an understanding of key information contained in the sheet. Any identified problems are rectified by the use of clear writing and by changing the way the PIS is laid out and designed. Further User Testing then tests whether the changes have led to improvements to the way the PIS performs. Three small, recent studies suggest that a combination of re-writing, design and testing results in a PIS that works much better to inform potential trial participants and which they prefer [13, 14, 15]. These studies have involved hypothetical settings, with participants being asked to imagine themselves being recruited to a trial, and what remains unknown is the effect of such changes to the PIS in actual trials. In particular, does an improved PIS impact on either of the quality of informed consent and the rate of recruitment?

3. Study details

The [Host trial name] study – [brief description of trial] - plans to use a [describe approach to recruitment] in recruiting patients. Potential participants will [describe approach to patients]. The NRES-approved PIS is x pages in length [any further info on PIS].

A revised PIS will be developed through User Testing. The content of the original PIS will be retained but it will be re-written and re-designed based on the outcomes of the User Testing process. It would be useful to know if the revised PIS impacts on rate of recruitment and the

quality of informed consent, in comparison with the original PIS. A nested randomised controlled trial would be the best approach to evaluate its effects.

4. Research Objectives

- 4.1 To establish if the number of patients recruited in to [*Host trial name*] is improved by the use of a participant information sheet developed through User Testing, compared to routine participant information sheet.
- 4.2 To explore whether user testing of the PIS improves retention in [Host trial]
- 4.3 [To establish if the quality of informed consent given by those patients who consent to be included in the trial is affected by the type of participant information sheet they initially receive] – delete as appropriate.
- 4.4 [To explore whether the reasons patients give for consenting or declining to participate in the [Host trial name] are affected by the type of participant information sheet they receive] – delete as appropriate

5. Method

5.1 Design

The proposed study will use a *[design of host trial]* design. Patients who are to be offered participation in the trial will be randomly allocated to one of two interventions:

a) sent the original [host trial] participant information sheet (see Appendix 1);

b) sent the user tested participant information sheet (see Appendix 2).

5.2 Inclusion / exclusion criteria

The recruitment trial will include all patients identified as potentially eligible for the [Host trial] study: there are no additional inclusion or exclusion criteria.

5.3 Recruitment and Randomisation

Potential participants in the [Host trial] study will be identified by [describe process of identifying potential participants]. All potentially eligible patients will [describe process for contacting patients and the point at which the PIS will be introduced]. The type of PIS included in each pack will be determined by random allocation using a method which is robust and ensures concealment of allocation, such as a computerised randomisation programme where feasible, conducted by someone independent from those undertaking recruitment. MRC START in [Host trial name] protocol v1.0 [date] [describe any specific aspects of randomisation process]. [Specify what data will be recorded by the host research team and how]. .

5.4 Intervention

The original participant information sheet for the [*Host trial*] study (see Appendix 1) was written in accordance with NRES guidance. It is presented as [*describe existing PIS*]. It was approved by an NHS REC as part of the application to conduct the [*Host trial*] study.

The revised participant information sheet will contain the same content as the original version but will differ in the way that the information is laid out, written and presented. It will be developed through User Testing with members of the public selected to reflect the target patients for the PIS, who will read and then be asked to find and show an understanding of key facts contained in the PIS. The testing will be undertaken in several rounds: the first round testing the original PIS; then several rounds with different iterations of the revised PIS until we were confident that the PIS could perform well to inform potential trial participants.

5.5 Outcome measures

The primary outcome will be the number of patients recruited to [*Host trial name*]. We will keep a record of all patients who were identified as potential participants and which intervention group they were in.

Secondary outcomes will be: [Secondary outcomes relate to different trial settings and studies which choose to include additional measures]

- The proportion of recruited patients who are retained to the end of the end of [host study name] or the number remaining in the study six months prior to the end of the MRC START programme
- the proportion of patients in each intervention group who agree to participate in [Host trial] (where this differs from the number actually recruited, due to eg exclusion criteria); delete as appropriate
- [the proportion of patients who decline to participate, who endorse the 'not understanding enough about the study' as a reason (see Appendix 5), according to each intervention group] – delete as appropriate;

MRC START in [Host trial name] protocol v1.0 [date] Page 4 of 9 Quality of Informed Consent data (specify measure?) (see Appendix 6), among patients who consent to take part, according to each intervention group] - delete as appropriate.

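### The retention outcome is a proportion of recruits or a raw count, with no rule for choosing; the count rises with recruitment alone, and the two can point in opposite directions.

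*Protocol*

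**What the plan says.** Objective 4.2 in the Protocol is "To explore whether user testing of the PIS improves retention in" the host trial. Unlike objectives 4.3 and 4.4, it is not marked as optional.

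The matching secondary outcome in section 5.5 is a single bullet with two alternatives:

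- "The proportion of recruited patients who are retained to the end of the end of" the host study;
- "or the number remaining in the study six months prior to the end of the MRC START programme".

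It is the only secondary outcome there without an instruction to delete as appropriate. It does not say that the result is given by PIS group, although objective 4.2 implies this.

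On allocation, section 5.1 says "Patients who are to be offered participation in the trial will be randomly allocated to one of two interventions", and section 5.3 says "The type of PIS included in each pack will be determined by random allocation". Randomisation therefore comes before recruitment to the host trial. Section 5.5 also says "We will keep a record of all patients who were identified as potential participants and which intervention group they were in", so the number randomised to each sheet will be known. Section 6.2 describes an analysis for returned consent forms only.

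**The concern.** The two halves of the bullet differ in three respects: the measure (proportion or number), the denominator (recruited patients or none stated) and the time point (host-trial end or a date tied to the programme). Nothing says when each is used.

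Each half also has its own fault as an answer to objective 4.2. The number remaining is recruitment multiplied by retention, so a sheet that only raises recruitment will appear to raise retention. The proportion is taken among recruits, a group formed after randomisation by the very thing the sheet is meant to change. If a better sheet brings in patients who are less likely to stay, the proportion falls even though no individual's retention has changed.

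The conclusion on retention can therefore depend on which half is reported. The document is a template, so the ambiguity passes to each host trial that uses it. Section 10 says the data go into a programme-wide meta-analysis. Section 6.2 names only response rates for pooling, but if retention is pooled too, host trials could supply measures that are not equivalent.

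**Working it through.** **The plan's own figure.** The protocol gives no figure for retention. Its only design figure is in section 6.1: 400 patients approached per arm, 80% power, a 10% difference, alpha 0.05. I read the difference as percentage points and the test as two-sided; the base rate is not stated. With pooled variance,

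n = [1.96·√(2p̄(1−p̄)) + 0.842·√(p₁(1−p₁) + p₂(1−p₂))]² / (p₂−p₁)²

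gives 388 for 40% vs 50%, 392 for 45% vs 55% and 388 for 50% vs 60%. With continuity correction these become 408, 412 and 408. So 400 reproduces for base rates of 40% to 50%. It serves below only as the arm size.

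**Step 1: the count with retention unchanged.** Let each arm have N randomised, recruitment rate r and retention rate among recruits k. The number remaining is N·r·k. At the design effect, extra recruits = 0.10 × 400 = 40. With k = 90% in both arms (assumed), extra patients remaining = 40 × 0.90 = 36, whatever the base rate. The proportion of recruits retained is 90% in both arms.

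**Step 2: opposite directions.** Assumed counts, 400 per arm, base recruitment 20%:

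- Original PIS: 80 recruited, 72 retained.
- Revised PIS: the same 80 (72 retained) plus 40 further recruits, of whom 70% stay (28). Total 120 recruited, 100 retained.

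| Measure | Original | Revised | Revised sheet looks |
|---|---|---|---|
| Proportion of recruits | 72/80 = 90.0% | 100/120 = 83.3% | worse (−6.7 points) |
| Number remaining | 72 | 100 | better (+28) |
| Recruited and retained, of all randomised | 72/400 = 18% | 100/400 = 25% | better (+7 points) |

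Wald 95% intervals:

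- Among recruits: SE = √(0.9×0.1/80 + 0.833×0.167/120) = 0.0478, so −6.7 points (−16.0 to +2.7).
- Over all randomised: SE = √(0.18×0.82/400 + 0.25×0.75/400) = 0.0289, so +7.0 points (+1.3 to +12.7).

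**Step 3: when the reversal occurs.** With equal arms, the count favours the revised sheet when r₁/r₀ > k₀/k₁. If k₁ < k₀ as well, the proportion points the other way. Here r₁/r₀ = 120/80 = 1.5 and k₀/k₁ = 0.900/0.833 = 1.08, so both conditions hold.

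**Step 4: sensitivity to the assumed retention of the 40 further recruits.**

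| Their retention | Proportion of recruits (original 90.0%) | Number remaining (original 72) |
|---|---|---|
| 70% | 100/120 = 83.3% | 100 |
| 80% | 104/120 = 86.7% | 104 |
| 90% | 108/120 = 90.0% | 108 |

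At 90% the proportions agree and correctly show no difference, while the count still shows a gain of 36.

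**Step 5: no denominator.** With 380 and 420 randomised (assumed), and 10% recruitment and 90% retention in both arms, the expected numbers remaining are 380×0.1×0.9 = 34.2 and 420×0.1×0.9 = 37.8. They differ with no effect of any kind.

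**The case against.** The best defence is that *or* is only a fallback date. A template must serve host trials that outlast the programme, and the second half names a programme date. On that reading each host trial uses one half, fixed by its timetable, and nobody chooses after seeing the data. This is plausible, and the protocol does not suggest a choice made on results. It does not remove the fault, because the wording changes the measure from a proportion to a count along with the date, and no rule is written down.

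It is also fair to say that the objective is exploratory, that retention among recruits is a natural descriptive reading of retention, and that analysis detail may sit in an analysis plan that is not shown. These limit the weight of the point. However, the protocol itself defines this outcome, and defines it in two ways.

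The reversal in the illustration depends on assumed counts, and the interval among recruits includes zero. That stands: it shows what can happen and does not predict it. The fault in the count needs no such assumption about marginal recruits (Step 4, last row).

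Two stronger readings are tempting and are not supported:

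- A reader might infer that neither measure compares randomised groups. That is true of the proportion among recruits only. The count by allocated arm implicitly includes everyone randomised, since those not recruited count as not remaining. With equal arms, or divided by the number randomised, it is a randomised comparison. Its fault is that it mixes recruitment with retention and states no denominator.
- A reader might infer that a calendar cut-off biases the comparison because late recruits have short follow-up. Both arms share the cut-off, so concurrent random allocation should roughly balance follow-up. It blurs the absolute figure more than the contrast.

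**Conclusion.** The point holds. Section 5.5 gives one outcome two non-equivalent definitions with no rule for choosing, and the raw number cannot answer objective 4.2. At the protocol's design effect, with an assumed 90% retention in both arms, the count shows 36 more patients remaining when retention is identical. The proportion among recruits is usable as a description but is not a comparison of the groups as randomised. The two disagree in direction in the assumed example (90.0% vs 83.3%, against 72 vs 100).

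Dividing by all randomised patients does not by itself isolate retention. In the same example, 18% vs 25% is a valid randomised comparison, but of being recruited and retained jointly. No single figure answers the question, which is why two are needed, each labelled for what it is.

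The conclusion rests on reading 10% as percentage points and on the assumed counts. The outcome is exploratory and the primary comparison is untouched, so this should be corrected but does not threaten the trial.

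**What to change.** In section 5.5, delete the number remaining and use proportions throughout, by PIS arm, at one time point set in advance: the end of the host trial or, if the host trial runs beyond it, the programme date already named. Report both of these:

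- (a) the proportion of recruited patients retained at that time, labelled as a non-randomised comparison that describes retention;
- (b) the proportion of all patients randomised to each sheet who are recruited and retained at that time, labelled *recruited and retained*, as the randomised comparison.

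The denominator for (b) is available from the record of all potential participants by group. Retention status at the chosen time should be listed in section 5.3, where the data to be recorded by the host team are still a placeholder; the protocol does not say that withdrawal data will be supplied.

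The cost is a change of wording, one extra calculation and possibly one extra data item from the host trial.

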6.1 Sample size

START is powered to detect a significant improvement in recruitment rate, defined as an increase in response of 10%. 400 patients per arm are required to provide 80% power to detect a 10% difference (alpha 0.05). Involvement in START has therefore been restricted to RCTs that will appraoch at least this many patients (note this is the number approached, not the number randomised: the former will often be many times higher than the latter).

[*Host trial*] is powered on recruiting XXX participants. Based on ??? it is predicted that XXX invitation letters will be sent, of which around XX% (XXX) will respond positively [*further details* of sample size if available].

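### The optional decline-reason outcome compares the arms only among decliners, a group formed after randomisation that the revised sheet is expected to change, so it can hide or reverse a change in refusals for lack of understanding

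*Protocol*

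**What the plan says.** Protocol section 5.1 sets the point of randomisation: "Patients who are to be offered participation in the trial will be randomly allocated to one of two interventions". Allocation therefore comes before the decision to accept or decline.

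Section 5.5 lists, in brackets and marked as deletable, an outcome defined as "the proportion of patients who decline to participate, who endorse the" reason of not understanding the study well enough, by intervention group. The reasons come from the decline form in Appendix 5. The bullet just above it uses a different denominator: "the proportion of patients in each intervention group who agree to participate in [Host trial"]. The same section also states: "We will keep a record of all patients who were identified as potential participants and which intervention group they were in".

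The matching objective, 4.4, is optional too: "To explore whether the reasons patients give for consenting or declining to participate" are affected by the sheet received. Section 6.1 powers the trial for a recruitment improvement "defined as an increase in response of 10" per cent, with 400 patients per arm, 80% power and alpha 0.05.

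**The concern.** Declining is a consequence of the sheet. If the revised sheet raises recruitment as hoped, it changes how many patients decline and probably which ones. Comparing reasons among decliners then sets two differently selected groups side by side, and randomisation no longer protects the comparison. Objective 4.4 nevertheless asks whether reasons are affected by the sheet, which is a question about its effect.

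What is at stake is the reading of one optional outcome on the route by which a clearer sheet might help. The share among decliners could stay level, or rise, while fewer of the patients sent the revised sheet refuse for want of understanding. Because the document is a template, the definition passes to every host trial that keeps the bullet.

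**Working it through.** **Inputs.** From the protocol: 400 per arm, 80% power, alpha 0.05, and a 10% gain (section 6.1). Assumed, because the protocol gives no figures: baseline recruitment of 5% to 70%, and 10% to 40% of decliners endorsing the reason under the original sheet. Also assumed: a two-sided test, the 10% read as 10 percentage points, and, in the second and third checks below, every patient not recruited counted as a decliner who states a reason.

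**The plan's own figure.** n per arm = [1.960 × √(2p̄(1−p̄)) + 0.842 × √(p₁(1−p₁) + p₂(1−p₂))]² / (p₂−p₁)². For 45% v 55%: (1.960 × 0.7071 + 0.842 × 0.7036)² / 0.01 gives 392, or 412 with continuity correction. For 40% v 50% and 50% v 60% it gives 388 (408). So 400 is reproduced for baselines near one half, on the absolute reading of 10%.

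**When the written outcome shows a benefit.** Let d be decliners and e be endorsing decliners, with 0 for the original sheet and 1 for the revised. The written outcome falls only if e₁/d₁ < e₀/d₀, that is, if e₁/e₀ < d₁/d₀. Lack-of-understanding refusals must fall proportionately faster than refusals overall. The whole-arm figure e/400 falls whenever e falls.

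**Three patterns, each with a 10-point recruitment gain (40 fewer decliners per 400).**

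| Pattern (assumed baseline recruitment; endorsing share) | Among decliners: original v revised | Of all allocated: original v revised |
|---|---|---|
| All refusals fall in proportion (10%; 20%) | 72/360 = 20% v 64/320 = 20% | 72/400 = 18% v 64/400 = 16% |
| All refusals fall in proportion (50%; 40%) | 80/200 = 40% v 64/160 = 40% | 80/400 = 20% v 64/400 = 16% |
| These refusals fall half as fast as refusals overall (50%; 40%) | 80/200 = 40% v 72/160 = 45% | 80/400 = 20% v 72/400 = 18% |
| Only these refusals fall (10%; 20%) | 72/360 = 20% v 32/320 = 10% | 72/400 = 18% v 32/400 = 8% |

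In the proportionate pattern the masked fall is the endorsing share times 10 points, so 1 to 4 points over the assumed 10% to 40%.

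**A decline-form example, also assumed.** With 400 per arm, let 100 forms come back under the original sheet (20 endorsing) and 60 under the revised (12 endorsing).
- Among forms: 20/100 = 20% v 12/60 = 20%.
- Of all allocated: 20/400 = 5.0% v 12/400 = 3.0%.
- Test: z = 0.020 / √(2 × 0.04 × 0.96 / 400) = 0.020 / 0.01386 = 1.44, p about 0.15.
- Relative risk 0.60, 95% CI about 0.30 to 1.21.

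**The same forms from a different cause.** Suppose 200 patients decline in each arm and 20% endorse the reason in each, but forms come back from 50% (100/200) v 30% (60/200). The counts are again 20/100 and 12/60. Here the level 20% v 20% is right, and 5.0% v 3.0% is a false benefit.

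**Precision.** At 400 per arm, power with the whole-arm denominator is about 11% for 18% v 16% and about 31% for 20% v 16%.

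**The case against.** The strongest objection is that the whole-arm figure brings a bias of its own. Patients who return no form count as not endorsing, so a difference in form return between the arms feeds straight into the comparison, as the last example shows. This stands. It is why the whole-arm figure cannot be read without the return rates, and why reporting those rates describes the problem but does not remove it. It does not rescue the written outcome, which depends both on who declines and on who returns a form.

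Second, masking is not inevitable. The revised sheet keeps the same content and presents it more clearly, so it may act mainly on lack-of-understanding refusals, and then the written outcome shows the benefit (20% v 10% in the table). In the decline-form example, exact masking needs forms giving other reasons to fall from 80 to 48, also by 40%. This stands and limits the claim to what can happen.

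Third, objective 4.4 is exploratory, and the mix of reasons among decliners is a fair descriptive answer to part of it. This also stands, and the share should be kept for that purpose. It does not answer whether the sheet affects such refusals.

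Fourth, the bullet could be read as declining and endorsing, out of everyone in the arm. The contrast with the bullet above makes the decliner reading more natural. If the other was meant, the same edit settles it.

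A reader might carry the criticism over to the Quality of Informed Consent outcome, taken "among patients who consent to take part, according to each intervention group". The protocol does not support calling that an error. Objective 4.3 openly limits its question to consenters, and section 6.2 already plans the proportion returning consent forms in each arm. What remains is a caveat on interpretation, which an analysis plan may carry.

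**Conclusion.** The point holds in a limited form. The decline-reason outcome, as defined in section 5.5, conditions on a group formed after allocation that the trial itself expects to change. It can, but need not, hide or reverse a change in refusals for lack of understanding. Under a 10-point recruitment gain and the assumed baselines, a fall of 1 to 4 points per patient allocated would go unseen if all refusals fall together. If these refusals fall half as fast as the rest, the outcome can move the wrong way (40% to 45%).

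A reader might infer that the decline-form example demonstrates a 40% reduction (5.0% to 3.0%). It does not. The counts are invented, the difference is statistically inconclusive, and a lower return rate alone could produce it. Nor is the trial's main result in doubt: the primary outcome, the sample size and the planned meta-analysis do not use this measure. As the outcome is optional, secondary and exploratory, the priority is low.

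**What to change.** Reword the bullet in section 5.5 so that the between-arm comparison is the number of patients who decline and give insufficient understanding of the study as a reason, divided by all patients allocated to each sheet. Report the difference with a 95% confidence interval.

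Keep the share among decliners as a descriptive figure, shown with the number declining and the decline-form return rate in each arm. Add one sentence saying that patients who return no form count as not endorsing, so the whole-arm comparison must be read beside the return rates.

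The cost is a change of wording. Section 5.5 already records the whole-arm denominator, and any host trial that keeps this outcome collects the numerator on the decline form. The return rate needs only a count of forms by arm. Given the low power shown above, the result should be presented as an estimate with its interval and not as a test of how the sheet works.

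### The optional decline-reason outcome in 5.5 is a share of patients who decline, a group formed after randomisation, so the difference between arms is not a randomised comparison and can move either way

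*Protocol*

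**What the plan says.** Protocol 5.5 lists, among the secondary outcomes, "the proportion of patients who decline to participate, who endorse the 'not understanding enough about the study' as a reason", by intervention group, with the reason taken from the decline form (Appendix 5, not shown). On a plain reading, the words "the proportion of patients who decline to participate, who endorse the" make patients who decline the denominator. The item is marked for deletion where not wanted, and the list is introduced with the note "Secondary outcomes relate to different trial settings and studies which choose to include additional measures".

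The matching objective, 4.4, is also optional. It is "To explore whether the reasons patients give for consenting or declining to participate in the" host trial "are affected by the type of participant information sheet they receive". Objective 4.1 asks whether the number recruited "is improved by the use of a participant information sheet developed through User Testing, compared to routine participant information sheet".

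The item above it in 5.5 takes whole arms as its base: "the proportion of patients in each intervention group who agree to participate". Section 5.5 also says that every potential participant will be recorded with the intervention group. Section 6.2 specifies a difference and 95% confidence interval for consent-form return only, not for decline reasons.

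**The concern.** Whether a patient declines is settled after the sheet has been sent, and the trial exists because the sheet may change that decision. Patients who decline in the two arms are therefore not exchangeable groups. A share calculated within them mixes two things: how many patients decline for not understanding, and how many decline for anything else.

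Objective 4.4 asks whether reasons are affected by the sheet. Under the present definition a difference could be read as an effect on understanding when only the mix of decliners has changed. A host trial that keeps the item inherits this denominator. It is written into the outcome definition, so it is not a detail left to an analysis plan.

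**Working it through.** **Inputs from the protocol (6.1).** 400 patients approached per arm, a 10% difference, 80% power, alpha 0.05.

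**Inputs not given, so assumed.** Two-sided alpha; baseline recruitment from 10% to 70% (6.1 leaves it as a placeholder); 20% of decliners endorsing the reason with the original sheet; every non-recruited patient counted as a decliner with a known reason.

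**The plan's own figure.** n per arm = [1.96 × √(2p̄(1−p̄)) + 0.842 × √(p₁(1−p₁) + p₂(1−p₂))]² / (p₂−p₁)², where p̄ is the mean of p₁ and p₂.
- 45% v 55%: 392 (412 with continuity correction), so the stated 400 is reproduced.
- 10% v 20%: 199, so 400 is more than enough at a lower baseline.
- A relative 10% increase (50% v 55%) would need 1565, so the target is read as 10 percentage points.

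Section 6.1 says that the number approached will often be many times the number randomised. A low baseline such as 10% v 20% fits that remark better than 45% v 55%, although the latter is the case that matches 400.

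**The outcome with endorsers unchanged.** Let D = 400 × (1 − recruitment rate) and let E be the number of endorsers. The planned outcome is E/D; the all-allocated alternative is E/400.

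| Recruited | D | E | E/D | E/400 |
|---|---|---|---|---|
| 10% v 20% | 360 v 320 | 72 v 72 | 20.0% v 22.5% | 18.0% v 18.0% |
| 30% v 40% | 280 v 240 | 56 v 56 | 20.0% v 23.3% | 14.0% v 14.0% |
| 45% v 55% | 220 v 180 | 44 v 44 | 20.0% v 24.4% | 11.0% v 11.0% |
| 70% v 80% | 120 v 80 | 24 v 24 | 20.0% v 30.0% | 6.0% v 6.0% |

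**Break-even.** E/D is equal in the two arms when E₁/E₀ = D₁/D₀. The fall in endorsers needed before E/D improves is 1 − 320/360 = 11.1%, 1 − 240/280 = 14.3% and 1 − 180/220 = 18.2% in the first three rows. These thresholds do not depend on the assumed 20%. Example at 45% v 55%: if endorsers fall from 44 to 40, E/D rises from 20.0% to 40/180 = 22.2%, while E/400 falls from 11.0% to 10.0%.

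**The opposite direction.** At 10% v 20%, 40 patients move from declining to joining.
- If 8 of them (20%) would have endorsed the reason, E/D is 64/320 = 20.0%, no change.
- If 12 (30%) would have, it is 60/320 = 18.8%, a fall.

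E/D can also fall with endorsers unchanged if the counted group grows. Suppose only returned decline forms count, with assumed return by 30% v 40% of decliners: 0.30 × 360 = 108 forms v 0.40 × 320 = 128. With 20% of 108 = 21.6 expected endorsers in each arm, the outcome reads 20.0% v 21.6/128 = 16.9%, while 21.6/400 = 5.4% in both arms.

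**Size against sampling error, all reasons known.**
- 10% v 20%: SE = √(0.20×0.80/360 + 0.225×0.775/320) = 3.1 points, against a gap of 2.5 (about 0.8 SE).
- 45% v 55%: SE = √(0.20×0.80/220 + 0.244×0.756/180) = 4.2 points, against a gap of 4.4 (about 1.1 SE).

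**Check on the alternative.** With the same 108 v 128 forms and 20% of forms endorsing in both arms, E/D is 20% v 20%, but E/400 is 21.6/400 = 5.4% v 25.6/400 = 6.4%. At 10% v 20% recruited, a relative rise in return rate above 360/320 − 1 = 12.5% is enough to produce such a difference.

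**The case against.** A reader might infer that success on the primary outcome necessarily pushes this outcome the wrong way. The documents do not support that. The revised sheet is meant to make information easier to find and understand, so it may well convert the patients who would have cited lack of understanding. If they make up more than the original-sheet endorsement share of those converted, the proportion falls. Nor is it established that the counted group must shrink: 5.5 separates agreeing from being recruited, and the reason is collected on a decline form, so those giving reasons could become more or fewer.

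A reader might also infer that the trial would go on to report harm to understanding. In the two cases checked, the artefact is about one standard error in a single host trial, and incomplete form return would add noise. Objective 4.4 is worded as exploratory, and no test or interval is set for this outcome.

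Nor is the contrast with the agreement outcome an inconsistency in itself. Retention is taken among recruited patients and consent quality among consenters, and asking decliners why they declined is a sensible descriptive question.

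Finally, the all-allocated measure has a weakness of its own: it counts patients who return no form as not endorsing, so it depends on form return, which the sheet may also affect.

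All of this limits the direction, size and weight of the point. It does not make the share among decliners a randomised comparison, and unlike a consent-quality score, this outcome can be defined for every allocated patient.

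**Conclusion.** The point holds as a minor one. Where the item is kept, the difference in shares among decliners cannot by itself show whether the sheet changed how many patients decline for not understanding, and its sign depends on which patients the sheet converts. With endorsers unchanged and a 10-point recruitment gain, the apparent worsening is 2.5 points at 10% v 20% recruited and 4.4 points at 45% v 55%. Those sizes rest on the assumed 20% endorsement, on counting all non-recruited patients as decliners, and on recruitment rates that the protocol does not give. That the denominator is formed after randomisation rests on none of these assumptions.

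**What to change.** In 5.5, where the item is kept, define the between-arm comparison as the proportion of all patients allocated to each sheet who decline and give the not-understanding reason, with the difference and 95% CI. Beside it, report the share among decliners (descriptive only) and the decline-form return rate by arm. State that neither measure should be read as an effect on understanding if return rates differ by arm.

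The cost is a few lines of wording. The allocated denominator needs no new data, because 5.5 already records every potential participant's group, and return rates need only a count of returned forms. The downsides are smaller percentages and the counting of patients who return no form as not endorsing, which is why the return rates must be shown.
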